### Study Design

**Table 1 – Study design and medication dosage (mg)**

Week			Run-In (V0-V1)	Phase 1 (V1-V2)					Phase 2 (V2-V3)					Wash- Out (V3-V4)	
				1 - 5	6	7	8	9	10	11	12	13	14	15	
Group A	Younger*	Donepezil	P	1.25	2.5	2.5	2.5	2.5	2.5	1.25	2.5	2.5	2.5	2.5	
		Melatonin	P	3	3	3	3	3	3	3	3	3	3	3	
	Older	Donepezil	P	2.5	5.0	5.0	5.0	5.0	5.0	2.5	5.0	5.0	5.0	5.0	
		Melatonin	P	3	3	3	3	3	3	3	3	3	3	3	
Group B	Younger*	Donepezil	P	P	P	P	P	P	P	1.25	2.5	2.5	2.5	2.5	
		Melatonin	P	P	P	P	P	P	P	3	3	3	3	3	
	Older	Donepezil	P	P	P	P	P	P	P	2.5	5.0	5.0	5.0	5.0	
		Melatonin	P	P	P	P	P	P	P	3	3	3	3	3	

Key: \* Younger = children below 12 years of age or 80 lbs. weight, who start and end at a lower dose of donepezil, than the other Older children; P = Placebo

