**Donepezil**– Donepezil, which is regulated by the FDA as a pharmaceutical drug, is also well tolerated in this population (Hardan and Handen 2002; Chez et al. 2003; Buckley et al. 2011; Handen et al. 2011; Srivastava et al. 2011). Related studies using other acetylcholinesterase inhibitors, including rivastigmine (Chez et al. 2004) and galantamine (Ghaleiha et al. 2013) have also shown that this class of medications is well tolerated in ASD children. Studies of donepezil in related pediatric clinical populations, such as fragile X (Sahu et al. 2013) and general Pervasive Developmental Disorder (Doyle et al. 2006) have found similar levels of tolerance. To maximize tolerance, the dosage will be titrated, as is commonly done in clinical trials with autistic children (Hardan and Handen 2002; Buckley et al. 2011; Handen et al. 2011). Parents/legal guardians will be instructed to administer the donepezil (1 capsule) with the melatonin, 30 minutes before a consistent desired bedtime.

**Drug compounding** –Pine Pharmaceuticals will repack the liquid melatonin from Natrol® and compound the liquid placebo. The Stony Brook Pharmacy will repack 5 mg generic donepezil into 1.25 and 2.5 mg gelatin capsules and compound the placebo in identical gelatin capsules. Patients will be given 40 days’ worth of study medication.

**Treatment Randomization** – Patients who agree to participate after they pass the screening will be assigned a study ID. After the run-in phase, study subjects will be randomly assigned to Group A or B using a computer-generated randomization plan with blocking and stratification by gender and age group (Younger: children below 12 years of age or 80 lbs. weight; Older:  $\geq$  12 years or  $\geq$  80 lbs.).

**Treatment Blinding** – The study pharmacists at Stony Brook and at Pine Pharmaceuticals will be the only individuals informed of the randomization assignments and will be responsible for labeling study drug and maintaining a master list linking patients with treatment assignments. All other research staff and participants will be masked regarding treatment assignment. Masking of active and placebo treatments will be preserved by creating liquids and capsules and containers that appear identical.

**Study Medication Accountability** – Study medication used and unused will be monitored through a drug accountability form completed at visit 1, 2, and 3.

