### ***Analysis***

**Power** – This is an exploratory study. It will be powered only to detect a large superiority ( $d = 0.9$ ) of the combined medication treatment as compared to placebo on the primary outcome (ABC-Social) in Phase 1 of the study. With a proposed sample size of 60 (30 in each group) and 10% subject attrition, there will be 54 completers (27 in each group), and power is estimated to be 91.1% (2-sided test, 5% type 1 error rate)

**Statistical Analysis** - All statistical analyses will be performed according to an intention-to-treat principle on the full sample. A last-observation-carried-forward imputation strategy will be used for missing data. The primary analysis will consist of an independent samples *t*-test on the normally distributed ABC Social change score in Phase 1. This will be followed by an analysis of covariance (ANCOVA) controlling for any variables on which the two drug groups are found to differ at baseline. Analyses of other continuous outcome variables in Phase 1 will use a similar approach. Group differences on categorical outcomes (e.g., CGI) will be analyzed by Chi Square test. Exploratory analyses for within group changes in Phase 2 (e.g., testing whether Group A derives additional benefit from 5 extra weeks of active treatment, or whether Group B obtains any benefit from the change from placebo to active treatment) and during the Washout Phase (e.g., testing whether the effects of the medications do washout when withdrawn) will be analyzed by means of a paired sample *t*-test on the outcome variables of interest. All tests will be 2-tailed, with a  $p = .05$  considered significant, with no correction for multiple analyses in this exploratory study. Correlation coefficients will be used to explore the relation of biomarkers to baseline behavioral and sleep measures, again using  $p = .05$ . All analyses will be performed using SPSS 21.0 statistical software. There will be no interim analysis.

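### The Younger and Older strata overlap for children discordant on age and weight, and one capsule of a listed strength cannot make up the 5.0 mg donepezil step for Older children

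*Combined protocol and SAP*

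**What the plan says.** Treatment, Treatment Randomization: randomisation is blocked and stratified by gender and age group, with the age groups given as "Younger: children below 12 years of age or 80 lbs. weight; Older: $\geq$ 12 years or $\geq$ 80 lbs". The timing is also stated: "After the run-in phase, study subjects will be randomly assigned to Group A or B".

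Study Design, Table 1 key: Younger children are those "below 12 years of age or 80 lbs. weight, who start and end at a lower dose of donepezil, than the other Older children". The key gives no thresholds of its own for Older.

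Study Design, Table 1: the donepezil rows differ by the same two labels. The Younger rows step from 1.25 to 2.5 mg. The Group A Older row reads "Older Donepezil P 2.5 5.0 5.0", a step from 2.5 to 5.0 mg.

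Treatment, Donepezil: parents are "instructed to administer the donepezil (1 capsule) with the melatonin".

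Treatment, Drug compounding: the pharmacy will "repack 5 mg generic donepezil into 1.25 and 2.5 mg gelatin capsules and compound the placebo in identical gelatin capsules".

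Analysis, Statistical Analysis: "The primary analysis will consist of an independent samples" *t*-test on the Phase 1 change in ABC-Social, with no stratum term.

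**The concern.** There are two faults, linked by the Younger/Older label.

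1. **The strata are not a partition.** Stratified randomisation needs exactly one stratum per child. The complement of an 'or' rule is an 'and' rule, so two 'or' rules on the same pair of cut-offs must overlap. Here the stratum label is also the dose label. Staff and pharmacy could each follow the text and still place the same discordant child in different groups, one for randomisation and the other for dosing. The end doses of the two groups differ twofold in Table 1 (2.5 v 5.0 mg).

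2. **The capsule instruction does not account for one dose step.** The count of one capsule, together with the listed strengths, cannot make up the 5.0 mg shown for Older children. If the instruction were followed to the letter with those capsules, Older children on active treatment would not receive the tabulated amount, and that bears on what Phase 1 tests in them. The number of capsules must also be the same for active and placebo if masking is to hold, and the text does not settle that number.

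**Working it through.** **The plan's own figure.** Inputs from the Power paragraph: d = 0.9, 60 children, 10% attrition, two-sided 5%. Completers: 60 × 0.9 = 54, or 27 per group. Normal approximation: power = Φ(d√(n/2) − 1.96) = Φ(0.9 × √13.5 − 1.96) = Φ(3.307 − 1.960) = Φ(1.347) = 0.911. This reproduces the stated 91.1%; the noncentral t calculation gives 90.1%. Neither stratum membership nor capsule strength enters this calculation, so the finding does not change it.

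**Strata.** 'Below' is read as applying to weight as well as to age. Each of the four age-by-weight cells is tested against both definitions in the randomisation paragraph, and then against the Table 1 key with Older taken as the remainder:

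| Cell | Meets Younger | Meets Older | Table 1 key |
|---|---|---|---|
| <12 y, <80 lbs | yes | no | Younger |
| <12 y, ≥80 lbs | yes | **yes** | Younger |
| ≥12 y, <80 lbs | yes | **yes** | Younger |
| ≥12 y, ≥80 lbs | no | yes | Older |

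Two of the four cells meet both definitions.

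The intended rule cannot be recovered from the randomisation paragraph, because there are two ways to make it exclusive:

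- Keep Younger as written and take the rest as Older. In table order the cells become Younger, Younger, Younger, Older.
- Keep Older as written and take the rest as Younger. The cells become Younger, Older, Older, Older.

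The two repairs disagree on exactly the two discordant cells. The first matches the Table 1 key on the reading used here; the second does not.

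**Capsules.** Each donepezil step in Table 1 is set against one capsule of a listed strength (1.25 or 2.5 mg):

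| Group and step | One listed capsule supplies it? |
|---|---|
| Younger 1.25 mg | yes |
| Younger 2.5 mg | yes |
| Older 2.5 mg | yes |
| Older 5.0 mg | **no** |

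The most that one listed capsule supplies is 2.5 mg, and 2.5/5.0 = 50% of the Older step. With the listed strengths, 5.0 mg corresponds arithmetically to 5.0/2.5 = 2 or 5.0/1.25 = 4 capsules. The protocol has no instruction for more than one capsule and describes no 5 mg capsule. No week counts are used, because the columns of Table 1 are not cleanly aligned in the available text; the 5.0 mg value itself is clear.

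**The case against.** The strongest reply on the strata is that the Table 1 key already settles dosing. By contrasting Younger children with the remaining Older ones, it gives every child one donepezil row, so the overlap touches only the stratification label. The effect there is small: allocation is random within whatever stratum is used, any misclassification falls on both arms alike, and the primary test ignores strata. Nothing in the documents shows that a child would in fact be classified in two ways. Most of this stands, and the overlap alone would be a minor matter for the analysis. But the complement reading of the key is an inference, and the randomisation paragraph states a different, explicit Older rule. The key therefore does not resolve the overlap; it adds a second rule under the same name.

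On the capsules, the reply is that the instruction states a count and not an amount, and that the compounding paragraph does not say its two strengths are the only ones. An undivided 5 mg capsule might exist. It is fair that the conflict comes from combining three statements (count, strengths and Table 1), and that 50% is an arithmetic ceiling and not a forecast of under-dosing. But the text names 5 mg only as the source product to be repacked, and a further strength would have to be assumed. As written, the three statements do not fit together.

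It is also fair that these are two separate drafting faults. They belong together because both determine which donepezil amount a given child receives.

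**Conclusion.** Both parts hold and should be fixed. Two of four age-by-weight cells belong to both randomisation strata, and one of four group-by-step doses cannot be given as one capsule of a listed strength (at most 2.5 of 5.0 mg).

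The weight rests on two things: the stratum label also selects the dose row, and the capsule instruction is at odds with the 5.0 mg step. The effect of the overlap on the statistical analysis is minor by itself. Randomisation remains valid, the primary comparison is unstratified, and the sample size and power stand.

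The conclusion assumes that 'below' governs both cut-offs and that the listed strengths are those to be used. The point that stratum and dose row can differ further assumes the natural reading of the Table 1 key. The documents do not give the number of discordant or Older children, so the number affected cannot be stated.

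**What to change.** - Write one Younger/Older rule that is mutually exclusive and exhaustive, and use it word for word in Table 1, the randomisation paragraph and the randomisation specification.
- Say which visit's age and weight govern the rule. Eligibility is checked at screening, while randomisation follows the five-week run-in, so a child near a cut-off could change group in between.
- Reconcile the capsule strengths and the number of capsules per administration with every donepezil step in Table 1, for active and matching placebo alike.

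The investigator and the pharmacy must decide which of the conflicting statements hold; no dose or cut-off is proposed here. The cost is protocol wording, the randomisation specification and a pharmacy sheet. No extra patients, visits or measurements are needed.

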#### **Outcome Measures**

Neurological Exam. At the Baseline visit and study visits V1-V4, a neurological exam will be performed, using the following template.

General Appearance: Is the child/adolescent well appearing? Are there any neurocutaneous lesions and/or dysmorphic features?

Neurologic: Cranial Nerve Exam:

CN II - Optic fundi and pupils are examined with response to light.

CN III, IV, VI - Extraocular movements are examined for dysconjugate movements and nystagmus.

CN V - Facial sensation is not tested.

CN VII - Is there facial weakness or asymmetry?

CN VIII - Is hearing intact to voice?

CN IX-XII - Is the palate was up-going, and the tongue was midline?

SENSATION: Overall not tested.

MOTOR SYSTEM: Muscle bulk, tone, and strength is tested by a combination of functional and manual tests for symmetry.

CEREBELLAR: Fine movements and movements of the limbs are assessed. The gait and the ability to tandem walk is assessed.

DEEP TENDON REFLEXES: Are reflexes normally active and symmetric?

**Lethargy/Social Withdrawal Subscale of the Aberrant Behavior Checklist (ABC-Social)** – the primary outcome measure will be the parent/legal guardian completed ABC-Social subscale (Aman et al. 1985a; Aman et al. 1985b). The ABC includes 58 items divided into five subscales (Irritability/Agitation, Lethargy/Social Withdrawal, Stereotypic Behavior, Hyperactivity/Noncompliance, and Inappropriate Speech) and requires approximately 10-15 minutes to administer. The ABC is a well-regarded measure that is widely used in ASD treatment studies and has good reliability and validity (Aman et al. 1985b; Rojahn et al. 2011; Kaat et al. 2013). The ABC has been used in a number of previous AChEI treatment studies, though most were open label trials (Hardan and Handen 2002; Niederhofer et al. 2002; Doyle et al. 2006; Nicolson et al. 2006; Niederhofer 2007; Ghaleiha et al. 2013). The ABC-Social subscale in particular has been found to be a useful and sensitive measure of treatment effects in this population (Scalhill et al. 2013).

**Stereotypic Behavior subscale of the ABC (ABC – Stereotypic)** The ABC will also provide a secondary outcome for the study, the Stereotypic Behavior subscale. This subscale is a well-regarded outcome measure of the restrictive and repetitive behaviors that are among the core symptoms of autism (Aman 2012).

**Children's Sleep Habits Questionnaire (CSHQ)** – This secondary outcome measure will assess sleep, using a brief seven item questionnaire adapted from the Children's Sleep Habits Questionnaire (CSHQ) (Owens et al. 2000). This parental questionnaire assesses sleep behaviors in children (Owens et al. 2000). It has been validated in children with ASD, correlates with polysomnographic recordings, and has been used successfully in previous studies of melatonin with such children (Malow et al. 2006; Leu et al. 2011; Goldman et al. 2012). The CSHQ items chosen for this study come from the subscales found to be most often disturbed in children with autism: Sleep Duration, Sleep Onset Delay, and Night Wakings (Goldman et al. 2012).

**Clinical Global Impressions (CGI)** – The blinded treating neurologist will complete this secondary outcome in order to assess overall clinical impressions of global improvement and medication efficacy (Guy 1976).

**Parent Reported Global Impressions (PRGI)** – Modeled on the CGI, parents/legal guardians will complete this secondary outcome in order to their overall impressions of global improvement and medication efficacy.

**Biomarkers** – A variety of convenient, non-invasive, and safe biomarkers will also be collected in order to better characterize the sample and to relate to baseline behavioral and sleep measures: prenatal history (including stressors and history of exposure to selective serotonin reuptake inhibitors or terbutaline), developmental neurological history and neurological exam, D2/D4 finger length ratio (from xerox of hand), and head circumference.

### ***Data safety and monitoring plan***

[name], who is unaffiliated with the current study, has volunteered to serve as our data safety monitor. [name] is an associate professor in the Neurology Department here at Stony Brook who is board certified by American Board of Sleep Medicine and the American Board of Psychiatry and Neurology. [name] will periodically randomly audit the protocol documentation with the first audit occur by the enrollment of the fifth subject in order to check the quality control of the investigation early in the process, and additional audits occurring an average of every 10 subjects. Among the important goals of the audits will be to ensure that adverse events are reported, protocol amendments are filed with the IRB, inclusion/exclusion criteria are followed, and the number of patient visits do not exceed the protocol guidelines.

### ***Analysis***

**Power** – This is an exploratory study. It will be powered only to detect a large superiority ( $d = 0.9$ ) of the combined medication treatment as compared to placebo on the primary outcome (ABC-Social) in Phase 1 of the study. With a proposed sample size of 60 (30 in each group) and 10% subject attrition, there will be 54 completers (27 in each group), and power is estimated to be 91.1% (2-sided test, 5% type 1 error rate)

**Statistical Analysis** - All statistical analyses will be performed according to an intention-to-treat principle on the full sample. A last-observation-carried-forward imputation strategy will be used for missing data. The primary analysis will consist of an independent samples *t*-test on the normally distributed ABC Social change score in Phase 1. This will be followed by an analysis of covariance (ANCOVA) controlling for any variables on which the two drug groups are found to differ at baseline. Analyses of other continuous outcome variables in Phase 1 will use a similar approach. Group differences on categorical outcomes (e.g., CGI) will be analyzed by Chi Square test. Exploratory analyses for within group changes in Phase 2 (e.g., testing whether Group A derives additional benefit from 5 extra weeks of active treatment, or whether Group B obtains any benefit from the change from placebo to active treatment) and during the Washout Phase (e.g., testing whether the effects of the medications do washout when withdrawn) will be analyzed by means of a paired sample *t*-test on the outcome variables of interest. All tests will be 2-tailed, with a  $p = .05$  considered significant, with no correction for multiple analyses in this exploratory study. Correlation coefficients will be used to explore the relation of biomarkers to baseline behavioral and sleep measures, again using  $p = .05$ . All analyses will be performed using SPSS 21.0 statistical software. There will be no interim analysis.

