**Table 2 – Visit procedures**

Visit no.	Person in charge	Screening	Baseline (V0)	V1	V2	V3	V4
Study weeks		/	0	5	10	15	17 – 27
Incl/excl criteria*	[name]	X					
Pregnancy test (if applicable)**	CRC nurse	X					
Informed consent and assent	Study coordinator	X					
Aberrant Behavior Checklist	Parent		X	X	X	X	X
Child's Sleep Habits Questionnaire	Parent		X	X	X	X	X
Parent Global Impressions	Parent		X	X	X	X	X
Prenatal, developmental, neurological history	[name]		X				
Neurological exam	[name]		X	X	X	X	X
Clinical Global Impressions	[name]		X	X	X	X	X
Adverse event monitoring	[name]			X	X	X	X
Head circumference	CRC nurse		X				
D2/D4 finger length ratio	CRC nurse		X				
Dispense study drug	[name]		X	X	X		
Sleep hygiene education	[name]		X				
Study drug accountability	Study coordinator			X	X	X	

\*Includes renal/hepatic function test if blood work was not done within the past month

\*\* For female patients who have started menses

Patients will meet with [name] for 5 visits (baseline, follow up visit 1-4) every 5 weeks:

**Phase 1** (between follow up visit 1 and 2) – The investigation will be conducted in 2 Phases as shown in Table 1. Phase 1 will be a double-blind randomized clinical trial using a parallel group design. It will assess the combined benefit of donepezil and melatonin in Group A versus placebo in Group B over 5 weeks.

**Phase 2** (between follow up visit 2 and 3) – Phase 1 will be followed by an exploratory Phase 2 in which both groups (A & B) will be placed on the active medications for an additional 5 weeks. Phase 2 will allow us to explore whether Group A derives any additional benefit from 5 extra weeks of treatment with the active medications, and whether Group B obtains any benefit from switching from placebo to the active medications.

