**Run-In Phase** (between visit 0/baseline and 1) – Phase 1 will be preceded by a Run-In Phase of 5 weeks where all subjects will receive placebo and instructions about how to improve sleep hygiene using the “Good Sleep Habits Checklist” (Durand 2014). Subjects and their families will be blinded to treatment during this phase, but investigators will not. The run-in will allow us to assess patient compliance with the study protocol. Only those who achieve compliance of at least 80% will be allowed to continue in the study and then be randomized to the two Groups. The Run-In will also allow us to control for any improvement due to better sleep hygiene. Finally, the Run-In will allow us to control for placebo effects, because the score obtained at the end of Run-In (possibly reflecting placebo effects) will be used as a baseline to which the scores at the end of each treatment phase can be compared.

**Wash-Out Phase** (between follow up visit 3 and 4) – A washout period of between 2 – 12 weeks will follow Phase 2, allowing us to explore any changes in both subject groups after active treatment has been withdrawn. The length of this period will vary in order to coincide with the next clinical visit of the patient with [name], recognizing that this data is of lower priority.

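### V2 is the only ABC-Social score in Phase 1 after randomisation, so full-sample LOCF sets the primary change to exactly zero for every child who misses it

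*Combined protocol and SAP*

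**What the plan says.** On who is analysed, the Statistical Analysis paragraph says: "All statistical analyses will be performed according to an intention-to-treat principle on the full sample". On missing values it says: "A last-observation-carried-forward imputation strategy will be used for missing data". The primary test is an unadjusted two-sample t-test on the Phase 1 change in ABC-Social. An ANCOVA follows, for variables that differ between the groups at baseline.

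The other pieces are in Study Design, Treatment and Outcome Measures:

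- Randomisation: "After the run-in phase, study subjects will be randomly assigned to Group A or B".
- Baseline: the Run-In Phase paragraph says that the end-of-run-in score "will be used as a baseline to which the scores at the end of each treatment phase can be compared". That visit is V1.
- Phase 1 window: "between follow up visit 1 and 2". Table 2 schedules the ABC at V0, V1, V2, V3 and V4, five weeks apart up to V3, with no visit between V1 and V2.
- Instrument: "the primary outcome measure will be the parent/legal guardian completed ABC-Social subscale", and the full ABC "requires approximately 10-15 minutes to administer".
- Power, for d = 0.9 and 30 per group with 10% attrition: "there will be 54 completers (27 in each group), and power is estimated to be 91.1% (2-sided test, 5% type 1 error rate").

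No ABC at early withdrawal is described, and no sensitivity analysis for missing data is planned.

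**The concern.** LOCF is usually defended because it uses the follow-up that a dropout did provide. Here no such follow-up is scheduled. The last value before V2 is V1, which is also the baseline, so the carried-forward change is V1 - V1 = 0. The rule amounts to assuming no change for every child without V2, in both arms. The plan neither says this nor tests it. The later ANCOVA adjusts for baseline imbalance and is not a check on the missing-data rule.

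The size of the estimate is at stake more than the significance test. The Background says that a positive signal may guide a larger follow-up study, so the estimated effect is one of the pilot's main products.

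**Working it through.** **Inputs from the plan.** d = 0.9; 30 randomised per arm; 27 completers per arm; two-sided alpha 0.05. No SD in points is given, so everything is in units of the SD of observed change (SD = 1). **Assumed:** placebo mean change m of 0 to 1.0 SD in the direction of improvement. Until step 6, missing children are assumed to change like others in their arm.

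**1. The plan's power.** Normal approximation: 0.9 x sqrt(27/2) - 1.96 = 3.307 - 1.960 = 1.347, and Phi(1.347) = 91.1%. This reproduces the stated figure. The exact noncentral t (52 df) gives 90.1%. Both are for a completer analysis of 54, not the LOCF analysis of 60.

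**2. Expected LOCF difference.** With a active and b placebo children lacking V2:

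(1 - a/30)(0.9 + m) - (1 - b/30)m

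At a = b = 3 this is 0.9 x 0.9 = 0.81, whatever m is. Simulating the planned t-test (200,000 trials) gives 0.810; observed children alone give 0.900.

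**3. Standardised by the imputed data.** The variance in an arm with mean change mu becomes 0.9 + 0.09 mu². For m = 0 to 0.5 the pooled SD is 0.968 to 1.000, so d is 0.81/0.968 = 0.84 to 0.81/1.000 = 0.81. In those units the shrinkage from 0.90 is about 7% to 10%.

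**4. Power and type I error at 3/3 (simulated).**

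| Placebo change m | LOCF power |
|---|---|
| 0 | 89.6% |
| 0.3 | 89.1% |
| 0.5 | 88.4% |
| 1.0 | 86.1% |

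The completer t-test gives about 90%. Type I error under LOCF is 4.6% to 5.1%.

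**5. Unequal dropout.** Six children lack V2. The probability is hypergeometric, for dropout unrelated to arm. The ranges run from m = 0 to m = 0.5.

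| Active/placebo missing | Probability | Estimate | Power |
|---|---|---|---|
| 3/3 | 33% | 0.81 | 90-88% |
| 4/2 | 24% | 0.78-0.75 | 87-82% |
| 2/4 | 24% | 0.84-0.87 | 92-93% |
| 5/1 | 8.5% | 0.75-0.68 | 84-74% |
| 1/5 | 8.5% | 0.87-0.94 | 94-96% |
| 6/0 | 1.2% | 0.72-0.62 | 81-64% |
| 0/6 | 1.2% | 0.90-1.00 | 95-98% |

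Example, 5/1 with m = 0.5: (25/30)(1.4) - (29/30)(0.5) = 1.167 - 0.483 = 0.68. Averaged over random splits, the estimate is 0.81, power 89-87% and type I error 5%. In the two extreme rows, type I error reaches about 6.6% if both arms share a 0.5 SD change.

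**6. Break-even at 3/3.** Suppose missing children would have kept a fraction f of their arm's change. The all-randomised effect is then 0.9(27 + 3f)/30 = 0.81 + 0.09f. LOCF (0.81) is off by -0.09f, and a missing-at-random analysis (0.90) by +0.09(1 - f). The errors are equal in size at f = 0.5.

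**7. Scale.** The standard error of the difference with 30 per arm is sqrt(2/30) = 0.258 SD, and 0.09/0.258 = 0.35.

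**The case against.** **The shift is small for a study of this size.** A third of a standard error will rarely change the reading of an exploratory pilot. For a follow-up with 90% power, n per arm = 2(1.96 + 1.28)²/d² is 26 at d = 0.90, against 30 to 32 at the LOCF d of 0.84 to 0.81. The pilot's own 95% interval around 0.9 (0.394 to 1.406) spans roughly 135 down to 11 per arm. This objection stands and sets the weight of the point.

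**Zero may be close to the truth.** Abstracts in the reference list give some support for children who stop drug. In an open melatonin trial in Asperger disorder, most of the behavioural gain disappeared after discontinuation. In an open controlled-release melatonin study of 25 children with autism, 16 returned to their pre-treatment score. In a donepezil trial in Alzheimer's disease, the groups did not differ significantly after a six-week placebo washout. A trial of melatonin and REM sleep in adults points the other way. None of these abstracts reports ABC-Social after stopping, and none covers a child who misses V2 while still on drug. They show that zero is plausible but do not establish it.

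**A missing-at-random analysis is no easier to test.** True: step 6 shows mirror-image errors. Changing the rule alone would swap one assumption for another. The case for change rests on collecting V2 from children who have stopped drug, so that any return to V1 is observed, and on reporting both assumptions for those still missing.

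**V1 might not be the reference.** The Run-In Phase paragraph says that it is. With V0 instead, the carried change would be V1 - V0 and not zero. V1 still precedes treatment, so the expected difference would remain 0.81.

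**Conclusion.** The point holds as a modest bias in the estimate. Under the plan as written, every randomised child without V2 contributes a change of exactly zero. At the plan's own attrition this shrinks the expected difference from 0.90 to 0.81 SD if missing children would have changed like their arm, and by nothing if they returned to V1. The documents cannot settle which is nearer, and the plan has no check on it.

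A reader might infer more, but the documents do not support these readings:

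- **A serious loss of power.** Putting 0.81 into the formula with 27 per arm gives 83-85%. That counts the dropouts twice: LOCF keeps 30 per arm, and the zeros also alter the SD. At equal dropout the simulated figure is 88-90% for a placebo change up to 0.5 SD, and about 86% at 1.0 SD.
- **An invalid test.** Type I error stays near 5% at equal dropout and on average over random splits.
- **A uniformly conservative rule.** With more placebo than active losses and a placebo change of 0.5 SD, the estimate can exceed 0.90.
- **The same harm in the Phase 2 and washout paired tests.** The Analysis section names no reference visit for these exploratory tests, so no firm size can be given.

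**What to change.** In the Analysis section:

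1. Seek the V2 ABC from the parent of every randomised child, including those who have stopped study drug.
2. Replace the LOCF t-test as primary with a V1-adjusted comparison of V2 (ANCOVA, likelihood-based or with multiple imputation by arm) under a stated missing-at-random assumption. Prespecify zero change, the present LOCF result, as a sensitivity analysis, and report missing V2 by arm.
3. Restate power as about 90% (exact t, unadjusted, 27 per arm) in place of 91.1%. Any gain from adjusting for V1 is separate and depends on a between-visit correlation that the plan does not give.

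**Cost.** SAP wording, minor programming, and one short parent form for about six families, if they agree. Each pair of forms recovered, one per arm, removes 0.9/30 = 0.03 SD of the possible bias under either rule. The downside is that the primary then relies on missing-at-random, which can overstate the all-randomised effect by up to 0.09 SD at 3/3. The zero-change analysis beside it shows that range.
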